14.2 Data safety monitoring plan

In compliance with the Washington University Institutional Data and Safety Monitoring Plan, the Principal Investigator will provide a Data and Safety Monitoring (DSM) report to the Washington University Quality Assurance and Safety Monitoring Committee (QASMC) semi-annually beginning six months after accrual has opened (if at least one patient has been enrolled) or one year after accrual has opened (if no patients have been enrolled at the six-month mark).

The Principal Investigator will review all patient data at least every six months, and provide a semi-annual report to the QASMC. This report will include:

- HRPO protocol number, protocol title, Principal Investigator name, data coordinator name, regulatory coordinator name, and statistician
- Date of initial HRPO approval, date of most recent consent HRPO approval/revision, date of HRPO expiration, date of most recent QA audit, study status, and phase of study
- History of study including summary of substantive amendments; summary of accrual suspensions including start/stop dates and reason; and summary of protocol exceptions, error, or breach of confidentiality including start/stop dates and reason
- Study-wide target accrual and study-wide actual accrual
- Protocol activation date
- Average rate of accrual observed in year 1, year 2, and subsequent years
- Expected accrual end date
- Objectives of protocol with supporting data and list the number of participants who have met each objective

- Measures of efficacy
- Early stopping rules with supporting data and list the number of participants who have met the early stopping rules
- Summary of toxicities
- Abstract submissions/publications
- Summary of any recent literature that may affect the safety or ethics of the study

The study principal investigator and Research Patient Coordinator will monitor for serious toxicities on an ongoing basis. Once the principal investigator or Research Patient Coordinator becomes aware of an adverse event, the AE will be reported to the HRPO and QASMC according to institutional guidelines.

14.3 Developmental therapeutics

Given the nature of this human gene transfer protocol, the principal investigator will monitor and analyze study data as they become available and will review this data on a monthly basis with the Developmental Therapeutics Group at the Siteman Cancer Center. This is an independent group that will provide more rigorous oversight than is routinely provided by the QASMC and the HRPO. The Director of the Developmental Therapeutics Group devotes 20% of their time to overseeing and managing early phase clinical trials. These trials consist of all phase 1 trials and selected Phase 2 trials. The Director will advise [name] in the proper conduct of this study and will review patient treatment and all toxicities in the weekly Phase 1 meeting. In addition, the Director will assist in the oversight of the regulatory and data management personnel involved in this clinical trial.

14.4 NIH Recombinant DNA Advisory Committee

14.4.1 Initiation of the clinical investigation

Appendix M-I-C-1 of the NIH Guidelines for Research Involving Recombinant DNA Molecules specify:

No later than 20 working days after enrollment (see definition of enrollment in Section I-E-7) of the first research participant in a human gene transfer experiment, the Principal Investigator(s) shall submit the following documentation to NIH OBA: (1) a copy of the informed consent document approved by the Institutional Review Board (IRB); (2) a copy of the protocol approved by the Institutional Biosafety Committee (IBC) and IRB; (3) a copy of the final IBC approval from the clinical trial site; (4) a copy of the final IRB approval; (5) a brief written report that includes the following information: (a) how the investigator(s) responded to each of the RAC's recommendations on the protocol (if applicable); and (b) any modifications to the protocol as required by FDA; (6) applicable NIH grant number(s); (7) the FDA Investigational New Drug Application (IND) number; and (8) the date of the initiation of the trial. The purpose of requesting the FDA IND number is for facilitating interagency collaboration in the Federal oversight of human gene transfer research.

15 STATISTICAL CONSIDERATIONS

15.1 Study objectives and endpoints

This is a single institution, open-label randomized phase 1 trial of neoantigen DNA vaccine alone vs. neoantigen DNA vaccine plus durvalumab in triple negative breast cancer (TNBC) patients following standard of care therapy. Patients with newly diagnosed clinical stage II-III TNBC are eligible for enrollment. Patients will receive standard of care therapy including chemotherapy, surgery and radiation therapy as clinically indicated. Following standard of care therapy, patients will be randomized to receive either a neoantigen DNA vaccine alone, or a neoantigen DNA vaccine + durvalumab.

15.1.1 Primary objective

The primary objective is to assess the safety of neoantigen DNA vaccines given alone or in combination with durvalumab. Safety assessment will include both clinical observation and laboratory evaluation. Toxicity will be graded according to the National Cancer Institute Common Terminology Criteria for Adverse Events v4.03.

15.1.2 Secondary objectives.

The secondary objective is to measure the immune response to neoantigen DNA vaccines given alone, or in combination with durvalumab. The immune response will be measured in the peripheral blood by luminex assay, ELISPOT, and multiparametric flow cytometry.

15.2 Study design and sample justification

This is a single institution, open-label randomized phase 1 trial of neoantigen DNA vaccine alone vs. neoantigen DNA vaccine plus durvalumab in triple negative breast cancer (TNBC) patients following standard of care therapy. Patients with newly diagnosed clinical stage II-III TNBC are eligible for enrollment. Patients will receive standard of care therapy including chemotherapy, surgery and radiation therapy as clinically indicated. Following standard of care therapy, patients will be randomized to receive either a neoantigen DNA vaccine alone, or a neoantigen DNA vaccine + durvalumab

Twenty-four (24) eligible patients will be enrolled, and we expect that majority of them will receive the vaccine and will be eligible for evaluation.

15.2.1 Sample Size Calculations for Immunogenicity

A power analysis was performed using the paired t-test for over time differences (i.e., measures at Baseline vs. Day 1, Day 57) to test the first hypotheses that neoantigen DNA vaccines can induce and/or enhance neoantigen-specific T cell responses (e.g., the frequency of neoantigen-specific CD8 T cells in ELISPOT and multi-parameter flow cytometry). Assuming a moderate correlation between measures taken from the same individual, the designed sample size (n=24 patients) allows us 80% power at 1-sided 0.05 alpha level to detect a minimum of $0.5 \times SD$ for overtime changes. A power analysis was also performed using the 2-sample t-test for between-arm differences (i.e., measures at Day 113, Day 169) to test the second hypotheses that durvalumab will enhance the response to neoantigen DNA vaccines. We expect that the majority of the patients enrolled will remain in the study and lead to at least 10 evaluable patients/arm for such comparison. The designed sample size (n=10 patients/arm) provides us 80% power at 1-sided 0.05 alpha level to detect a minimum of $1.2 \times SD$ for between-group differences. Preliminary data from our phase 1 trial for mammaglobin-A DNA vaccine, though on patients with stable metastatic breast cancer and targeting a tissue-specific antigen, showed that the frequency of antigen-specific CD8 T cells can be measured with ~20% coefficient of variation ($CV=SD/Mean$). Therefore, the designed sample size allows us to detect ~10% for over-time differences and ~15% for between-group differences respectively. As a study to estimate preliminary information, we expect that ~20% difference will provide an adequate signal for immunogenicity. In addition, we anticipate that more power could be achieved because the actual data analysis will be performed using mixed model which uses data more efficiently and allows us to borrow information across multiple time points.

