4.6 Randomization

Twenty-four patients will be enrolled. Patients will be randomized for participation in a 1:1 ratio to receive either neoantigen DNA vaccine alone or neoantigen DNA vaccine plus durvalumab. The randomization table will be generated using the SAS program PROC PLAN. Randomization will take place after the manufacture of the vaccine and after eligibility has been reconfirmed.

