15.3.2 Immune response

Neoantigen-specific T cell response to neoantigen DNA vaccines + durvalumab is the secondary objective of the trial. Neoantigen specific T cell responses will be measured by Luminex, ELISPOT, multiparametric flow cytometry, and CyTOF. The frequency of antigen-specific CD8 T cells in each arm at each time will be summarized using means, standard deviations and medians. The change over time as well as the difference between arms will also be compared using linear mixed model for repeated measurement data. The immunogenicity of the neoantigen DNA vaccine will also be analyzed qualitatively by summarizing the phenotypic and functional characteristics of epitope-specific CD8 T cells. Responses will be considered positive if the number of T cells after vaccination is greater than two standard deviations above the mean before vaccination [101]. The frequency of positive responses at each time point will be assessed and binomial response rates with 95% confidence interval estimates will be presented. In addition to presenting the binomial response rates, graphical and tabular summaries of the underlying distributions will be made.

To determine whether the observed difference is larger than might be expected by chance, a permutation test will be used to compare the observed test statistic to the distribution of test statistics that would be seen if there were no difference between the two arms. Specifically, we will randomly shuffle the data and calculate the test statistic from the shuffled data. This procedure will be repeated 10,000 times and the resultant testing statistics will provide an accurate representation of the null distribution. The observed test statistics of between-arm differences will be compared to the null distributions. For each outcome, the permuted p-value will be the fraction of permuted samples that resulted in a small statistic than the original sample [103].

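### The stated ~15% detectable between-group difference does not follow from the plan's own inputs: 1.2 SD at a 20% CV is about 24%

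*Combined protocol and SAP*

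**What the plan says.** Section 15.2.1 sets out two power calculations, both at 80% power and a one-sided 0.05 level. A paired t-test on 24 patients is said to detect a change over time of 0.5 SD. A two-sample t-test at Day 113 and Day 169, expected to have "at least 10 evaluable patients/arm for such comparison", is said to detect a "minimum of $1.2 \times SD$ for between-group differences".

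The section then moves to percentages. Citing an earlier mammaglobin-A vaccine trial, it states that "the frequency of antigen-specific CD8 T cells can be measured with ~20% coefficient of variation", with CV defined as SD divided by mean. From this it infers that "the designed sample size allows us to detect ~10% for over-time differences and ~15% for between-group differences respectively". It goes on to say that a difference of about 20% would be a sufficient signal of immunogenicity. Last, it anticipates further power because "the actual data analysis will be performed using mixed model", and gives no figure for that gain.

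Section 15.3.2 confirms that the "difference between arms will also be compared using linear mixed model for repeated measurement data". Section 4.6 fixes the allocation: "Patients will be randomized for participation in a 1:1 ratio", with 24 patients in total, so 12 per arm if nobody is lost.

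**The concern.** The two percentages stand in one sentence and are presented as results of one conversion, SD multiple times CV. The first obeys that rule and the second does not. The second comparison tests the trial's second hypothesis, that durvalumab enhances the response to the vaccine.

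What is at stake is how a between-arm result is read. With 15% detectable, the trial would seem to have more than 80% power for the 20% difference the plan regards as sufficient, and a null comparison would count as fairly strong evidence against such an effect. If the detectable difference is in fact above 20%, that reading is not supported.

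**Working it through.** **Inputs, all from Section 15.2.1 unless noted**

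- Two-sample t-test, one-sided α = 0.05, 80% power
- n = 10 evaluable per arm; 12 per arm if all 24 patients are evaluable at 1:1 (Section 4.6)
- Detectable difference 1.2 SD between arms and 0.5 SD over time
- CV = SD/mean ≈ 20%, so 1 SD ≈ 20% of the mean

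**Step 1. Reproduce the SD multiple.** For a standardised difference δ and n per arm, power = P(T > t₀.₉₅,₂ₙ₋₂), where T is noncentral t with 2n − 2 degrees of freedom and noncentrality δ√(n/2). With n = 10 the critical value is 1.734 on 18 degrees of freedom. Power reaches 80% at δ = 1.156, which rounds to the plan's 1.2; at δ = 1.2 the power is 82.5%. The 1.2 SD is therefore sound.

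**Step 2. Reproduce the over-time percentage.** 0.5 × 20% = 10%, as stated. The 0.5 SD is itself a fair rounding: a paired t-test with n = 24 gives 0.523 SD at an assumed within-patient correlation of 0.5.

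**Step 3. Apply the same conversion between groups.** 1.2 × 20% = 24%; unrounded, 1.156 × 20% = 23.1%. The plan states about 15%. The ratio is 24/15 = 1.6, too large for rounding.

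**Step 4. What 15% would require.** 15%/20% = 0.75 SD. Alternatively, at 1.2 SD the CV would have to be 15%/1.2 = 12.5%.

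| Evaluable per arm | 80% power at | Power at 15% (0.75 SD) | Power at 20% (1.0 SD) |
|---|---|---|---|
| 10 | 1.156 SD = 23.1% | 48.8% | 69.4% |
| 12 | 1.048 SD = 21.0% | 55.4% | 76.7% |

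For 80% power at 0.75 SD, 22 per arm gives 78.9% and 23 per arm gives 80.5%, so 23 are needed. For 80% power at 1.0 SD, 14 per arm are needed.

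**Step 5. Look for a reading of the stated inputs that gives 15%.** A two-sided test gives 26.5% at 10 per arm and 23.9% at 12. Treating the CV on a log-normal scale at 1.2 SD gives +27% or −21%. None comes near 15%.

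**Step 6. Allow for pooling the two named visits.** Assume equal SD and equal effect at Day 113 and Day 169, use the mean of the two, and make no baseline adjustment. The detectable difference is then multiplied by √((1 + ρ)/2), where ρ is the correlation between visits.

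- 10 per arm: 23.1% × √0.75 = 20.0% at ρ = 0.5; 23.1% × √0.5 = 16.4% at ρ = 0 (carrying the unrounded 23.13%).
- 12 per arm: 18.1% at ρ = 0.5 and 14.8% at ρ = 0.

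At 10 per arm, the number the plan uses, no non-negative correlation brings the pooled figure to 15%.

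**The case against.** The strongest reply is that the planned analysis is a repeated-measures mixed model, not a single-visit t-test, and that such a model can get near 15%. This is correct as arithmetic. Suppose every pair of measurements has correlation 0.5, SDs and effects are equal, and the small loss of degrees of freedom is ignored. The mean of the two post-durvalumab visits has variance 0.75 (in SD² units). Adjusting for one pre-durvalumab measurement leaves 0.75 − 0.25 = 0.50, giving 16.4% at 10 per arm and 14.8% at 12. Adjusting for the mean of three leaves 0.75 − 0.25/0.667 = 0.375, giving 14.2% and 12.8%.

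This does not rescue the stated figure. The text derives the 15% from the t-test multiple and the CV, and only afterwards mentions the mixed model as an additional gain, without a number. Section 15.2.1 assumes a moderate correlation for the over-time test only, and Section 15.3.2 specifies no baseline adjustment. What stands is that the authors may be able to justify a figure near 15% by stating such a model, and that the t-test powers above leave out any gain from it.

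It is also fair to say that the endpoint is secondary, that the study describes its purpose as preliminary estimation, and that no stopping rule or other decision depends on the 15%. That limits the consequence but does not make the number right.

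A further qualification is that durvalumab-arm patients without a T cell response are replaced, with no matching rule in the vaccine-alone arm (Sections 8.2 and 8.3). In simulation at 10 per arm, assuming 80% respond and a correlation of 0.5 to 0.7 between the gating measurement and the outcome, the unadjusted t-test's one-sided false-positive rate rose from 5% to about 10–14%. Those assumptions are not in the documents and the matter is separate from this arithmetic, but it is why the powers quoted here must be labelled as ignoring that rule.

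**Conclusion.** The concern holds. By the plan's own conversion, the detectable between-group difference at 10 evaluable patients per arm is about 24% (23.1% unrounded), not 15%, and it is 21.0% if all 12 per arm are evaluable. Power for a true 15% difference is about 49% and 55% respectively. The correction moves the detectable difference from below the plan's 20% benchmark to above it, with power for 20% of about 69% at 10 per arm and 77% at 12.

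These results rest on a single-visit two-sample t-test, one-sided 0.05, and a 20% CV taken from another trial in a different setting; the percentages scale directly with that CV. The 1.2 SD, the 10 per arm, the over-time figure and the primary safety objective are not in question. The error should be fixed, but it does not threaten the design.

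**What to change.** In Section 15.2.1, replace the between-group figure of about 15% with about 24% (about 21% if all 12 per arm are evaluable). If 15% was intended, state the CV, the correlation or the model that yields it.

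Then add a sentence to this effect:

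> By the single-time-point two-sample t-test used for this power calculation, power for a between-arm difference of about 20% is about 69% with 10 evaluable patients per arm and 77% with 12. These are approximations that exclude any gain from the planned mixed model and ignore the replacement of durvalumab-arm non-responders (Sections 8.2 and 8.3).

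The cost is one less favourable figure and one labelled statement. Sample size, visits, samples and the planned analysis do not change.

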15.2.2 Sample Size Calculations for Safety

Sample size calculations for safety are expressed in terms of the ability to detect serious adverse events. The ability of the study to identify serious adverse events is best expressed by the maximum true rate of events that would be unlikely to be observed and the minimum true rate of events that would very likely be observed. Based on extensive simulations regarding the sample size for translational studies, [102] Piantadosi recommended that a sample size of 10 to 20 patients would provide a reasonable precision for estimating preliminary information. For example, there is 80% chance of observing at least 1 serious adverse event among a sample size of $n=10$ patients if the "true" AE rate is at least 15%. Conversely, if the "true" AE rate is less than 3%, there is 3% chance to observe 2 or more serious adverse events.

15.3 Data Analysis

15.3.1 Safety analysis

Safety evaluation is the primary objective of the trial. The data will be descriptive, and standard toxicity definitions and criteria will be used as outlined in the National Cancer Institute Common Terminology Criteria for Adverse Events version 4.03.

The number and percentage of subjects experiencing each type of adverse event will be tabulated by severity, and relationship to treatment. If appropriate, confidence intervals will be used to characterize the precision of the estimate. A complete listing of adverse events will also be tabulated, and will provide details including severity, relationship to treatment, onset, duration, and outcome.

Laboratory data measured on a continuous scale will be characterized by summary statistics (mean and standard deviation). Boxplots of laboratory data will be generated for baseline values and for values measured during and after protocol therapy at each specific time point. Contingency tables will also be used to describe the change of safe data over time as appropriate.

15.3.2 Immune response

Neoantigen-specific T cell response to neoantigen DNA vaccines + durvalumab is the secondary objective of the trial. Neoantigen specific T cell responses will be measured by Luminex, ELISPOT, multiparametric flow cytometry, and CyTOF. The frequency of antigen-specific CD8 T cells in each arm at each time will be summarized using means, standard deviations and medians. The change over time as well as the difference between arms will also be compared using linear mixed model for repeated measurement data. The immunogenicity of the neoantigen DNA vaccine will also be analyzed qualitatively by summarizing the phenotypic and functional characteristics of epitope-specific CD8 T cells. Responses will be considered positive if the number of T cells after vaccination is greater than two standard deviations above the mean before vaccination [101]. The frequency of positive responses at each time point will be assessed and binomial response rates with 95% confidence interval estimates will be presented. In addition to presenting the binomial response rates, graphical and tabular summaries of the underlying distributions will be made.

To determine whether the observed difference is larger than might be expected by chance, a permutation test will be used to compare the observed test statistic to the distribution of test statistics that would be seen if there were no difference between the two arms. Specifically, we will randomly shuffle the data and calculate the test statistic from the shuffled data. This procedure will be repeated 10,000 times and the resultant testing statistics will provide an accurate representation of the null distribution. The observed test statistics of between-arm differences will be compared to the null distributions. For each outcome, the permuted p-value will be the fraction of permuted samples that resulted in a small statistic than the original sample [103].

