The results of the completed HIV-1 ADVAX vaccine study in healthy subjects have been published [79]. As reported in the abstract, eight volunteers each received 0.2 mg, 1 mg, or 4 mg ADVAX or saline placebo via electroporation (EP), or 4 mg ADVAX via standard intramuscular injection at weeks 0 and 8. A third vaccination was administered to eleven volunteers at week 36. EP was safe, well-tolerated and considered acceptable for a prophylactic vaccine. EP delivery of ADVAX increased the magnitude of HIV-1-specific cell mediated immunity by up to 70-fold over IM injection, as measured by gamma interferon ELISpot. The number of antigens to which the response was detected improved with EP and increasing dosage. Intracellular cytokine staining analysis of ELISpot responders revealed both CD4+ and CD8+ T cell responses, with co-secretion of multiple cytokines. Briefly, results from this study indicate that EP-based delivery with the TDS-IM device at ADVAX DNA doses ranging from 0.2–4.0 mg was safe and effective in improving the magnitude, breadth and durability of cellular immune responses to a DNA vaccine candidate. Assessment of the tolerability of the EP procedure by questionnaire after each administration indicates that the procedure is generally acceptable for use in healthy subjects.

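### The percent detectable differences in section 15.2.1 are unsupported: the 20% CV comes from another antigen and population, and even at that CV the between-arm figure is about 24%, not 15%

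*Combined protocol and SAP*

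**What the plan says.** Section 15.2.1 contains two power calculations for the T cell response.

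- **Over time.** A paired t test is used on all 24 patients. "Assuming a moderate correlation between measures taken from the same individual", with no value given, the sample "allows us 80% power at 1-sided 0.05 alpha level to detect a minimum of $0.5 \times SD$ for overtime changes".
- **Between arms.** A two-sample t test is used at one-sided 0.05, with Day 113 and Day 169 named. Randomisation is 1:1 among 24 patients (section 4.6), and retention is expected to "lead to at least 10 evaluable patients/arm for such comparison". The stated detectable difference is 1.2 SD at 80% power.

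To turn SD units into percent, the section cites the mammaglobin-A DNA vaccine trial, whose data "showed that the frequency of antigen-specific CD8 T cells can be measured with ~20% coefficient of variation". It acknowledges that those patients had stable metastatic disease and that the target was a tissue-specific antigen. From this it concludes that about 10% over time and about 15% between groups can be detected, and it takes a difference of about 20% as an adequate immunogenicity signal. It then adds that the mixed model should bring further power.

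The analysis in section 15.3.2 reads: "The change over time as well as the difference between arms will also be compared using linear mixed model for repeated measurement data". A permutation test with 10,000 shuffles follows for the between-arm difference. Neither names a measurement scale.

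**The concern.** A percent detectable difference is the SD multiple times the between-patient CV, so it can be no better than the CV put in. The 20% is described as how well a frequency can be measured, for one antigen shared by all patients. In this trial each patient receives her own construct with up to 20 neoantigens (section 6.1). The spread that governs the between-arm comparison therefore also includes differences between patients, HLA types and epitopes. No figure for that spread appears in the documents.

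Separately, the two percent figures do not fit each other. If 0.5 SD is 10%, then 1.2 SD cannot be 15%.

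At stake is how a null or borderline durvalumab comparison will be read. A reader of section 15.2.1 would think that a 20% difference lies comfortably above the detection limit. On the plan's own inputs it lies below it.

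**Working it through.** **Inputs, all from section 15.2.1:** one-sided alpha 0.05; power 80%; n = 24 paired; n = 10 per arm; CV 20%. The within-patient correlation ρ is not given, so I take 0.5 and show 0.3 to 0.7.

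**1. Over-time figure (reproduces).** The SD of a paired difference is SD × √(2(1 − ρ)), which equals SD at ρ = 0.5. The noncentral t calculation for n = 24 gives a detectable change of 0.52 SD (0.51 by normal approximation), close to the stated 0.5. In percent, 0.523 × 20% = 10.5%. The range is 12.4% at ρ = 0.3 to 8.1% at ρ = 0.7. The stated 10% is consistent with this.

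**2. Between-arm SD multiple (reproduces).** With noncentrality d × √(10/2) and 18 degrees of freedom, 80% power needs d = 1.156. At d = 1.2 the power is 82.5%. The stated 1.2 SD is fair rounding.

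**3. Between-arm percent (does not reproduce).**
- Stated multiple: 1.2 × 20% = 24%.
- Exact multiple: 1.156 × 20% = 23.1%.
- With 12 per arm: 1.048 × 20% = 21.0%.
- Two-sided, 10 per arm: 1.325 × 20% = 26.5%.

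None of these gives 15%. To get 15% from 1.2 SD, the CV would have to be 15/1.2 = 12.5%.

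**4. Power at the percentages the plan names (CV 20%, two-sample t test).**

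| Difference | SD units | 10 per arm | 12 per arm | Needed per arm for 80% |
|---|---|---|---|---|
| 15% | 0.75 | 49% | 55% | 23 |
| 20% | 1.00 | 69% | 77% | 14 |

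**5. If the CV is not 20%.** Values above 20% are assumptions. For a log-normal outcome the log-scale SD is σ = √(ln(1 + CV²)). The detectable ratio is exp(1.156σ) between arms and exp(0.523σ) over time at ρ = 0.5.

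| CV | σ | Between arms | Over time | Between-arm power for a 1.2-fold ratio (log scale) |
|---|---|---|---|---|
| 20% | 0.198 | 1.26-fold | 1.11-fold | 63% |
| 50% | 0.472 | 1.73-fold | 1.28-fold | 21% |
| 100% | 0.833 | 2.62-fold | 1.55-fold | 12% |

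**The case against.** **The plan discloses the limits.** Section 15.2.1 admits the different population and antigen and describes the study as yielding preliminary information. Section 15.3.2 adds medians, distribution summaries and response rates with confidence intervals. This stands, and it keeps the point modest. It does not make 1.2 × 20% equal to 15%.

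**The mixed model may do better than the t test.** Reaching 15% at 80% power needs the variance cut to (15/23.1)² = 0.42 of its value. Averaging Day 113 and Day 169 at ρ = 0.5 gives (1 + 0.5)/2 = 0.75, so √0.75 × 23.1% = 20.0%. Adjusting for baseline as well gives 0.75 − 0.25 = 0.50, so 16.4%. At ρ = 0.7 it gives 0.85 − 0.49 = 0.36, so 13.9%. A gain of this kind is possible. However, the plan names no baseline adjustment and presents the mixed-model gain as additional to the 15%, so it cannot be where the 15% comes from. It also does nothing for the choice of CV.

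**A reader might infer that the data will be analysed untransformed, that power is thereby lost, and that a log analysis should be required.** The documents do not support this. Section 15.3.2 is silent on scale; it does not specify the raw scale. Under a permutation test on mean differences, the gain from logs in log-normal simulations is a few points: 77% against 81% at CV 65% for a doubling, and 51% against 56% at CV 100%. It reverses if some patients have zero counts. With 10% zeros assumed in both arms, CV 65% and a doubling, raw power is about 61% against 32% for the log of frequency plus a small constant. Sections 8.2 and 8.3 do anticipate patients without a response.

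**A reader might also take the documents to show fold-scale spread between patients.** They do not. The statement in section 6.9.4 that electroporation "increased the magnitude of HIV-1-specific cell mediated immunity by up to 70-fold over IM injection" is a delivery effect. The 1650 and 606 spot counts in section 7.2 are two peptides in mice. Section 6.9.1 even claims consistent responses between subjects with electroporation. A larger CV is plausible but remains an assumption.

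**Conclusion.** Two defects stand, of unequal firmness. The firm one is arithmetic: on the plan's own multiple and CV, the between-arm detectable difference is about 24%, not 15%. The 20% target then has about 69% power with 10 per arm, and 15% has about 49%. These powers assume the two-sample t test that section 15.2.1 names, equal SDs and a 20% CV.

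The second is lack of support. The 20% CV is taken from another antigen and population, and nothing in the documents shows that it holds between patients who each receive a different vaccine. Both percent figures scale directly with it, including the over-time 10%, which is otherwise correctly computed. How far the truth departs from 20% cannot be determined from the documents.

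The SD-unit calculations are sound. The point does not touch the primary safety objective, and it does not show that the planned analysis is invalid.

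**What to change.** In section 15.2.1:

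1. Correct the between-group figure from about 15% to about 24% at a 20% CV.
2. State that a 20% between-arm difference has about 69% power with 10 per arm by the two-sample t test.
3. Give the detectable effects in SD units (0.5 over time, 1.2 between arms), with matching fold changes over an assumed CV range. Between arms these are about 1.26-fold at 20%, 1.7 at 50% and 2.6 at 100%. Say that the range is assumed, and state the within-patient correlation used.

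Optionally, add a log-scale analysis to section 15.3.2 as a sensitivity analysis, with the rule for zero counts fixed in advance. It need not replace the planned analysis.

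The cost is wording only; enrolment, sampling and conduct are unchanged. The downside is that the stated detectable effects become less favourable, and the 20% signal is openly below 80% power for the durvalumab comparison.
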